2.3 RISK/BENEFIT ASSESSMENT

2.3.1 Known Potential Risks

Risks of Metreleptin:

Metreleptin was FDA-approved to treat the complications of leptin deficiency in patients with congenital and acquired lipodystrophy in 2014. Potential risks of metreleptin based on studies in patients with generalized and partial lipodystrophy, obesity, and other populations are summarized in the Prescribing Information (<http://www.myalept.com/prescribing-information>).

Key potential side effects are summarized below:

1. Injection site reactions: The most frequently reported adverse events in studies of metreleptin have been skin reactions (injection site reactions) at the site where the drug is injected. injection site reactions of erythema, pruritus, inflammation (induration), urticaria and edema were reported in 40% of subjects from the previous studies (compared to 15% of placebo-treated subjects) (Investigator's Brochure). The majority were reported as mild in severity with average time of onset of 15 days. All sites of injection (abdomen, arm and leg) used for the site of injection were affected. Higher doses appeared to have greater incidence and earlier onset (Investigator's Brochure). Biopsies of the injection site have been reported in the Investigator's brochure from 2 cases. The results were similar and consistent with a delayed hypersensitivity reaction to the protein (Investigator's Brochure).

Mild to moderate injection site ecchymosis was reported in 56% of all subjects, with a higher incidence occurring with subcutaneous bolus administration (as planned in this study) as opposed to administration with continuous infusion. There were no reported systemic symptoms to suggest a systemic allergic reaction. Some of the local reactions have been moderated with antihistamines, anti-inflammatory agents, topical steroids and cold compresses. In some subjects, investigators have reported gradual decreases in severity over time to complete disappearance of injection site reactions during continuous study-drug administration (Investigator's Brochure).

2. Hypersensitivity: Hypersensitivity reactions (e.g. anaphylaxis, urticaria, generalized rash) have been observed. Subjects who have a known history of anaphylaxis or anaphylactic-like reactions should not be administered Metreleptin. Also, subjects who have a known hypersensitivity to E. Coli derived proteins should not be administered Metreleptin because the Metreleptin protein is expressed in an E. Coli system.
3. Antibodies to recombinant human leptin: Development of anti-drug antibodies occurs in the majority of patients treated with metreleptin. In rare cases (<5%), antibodies with in vitro neutralizing activity to leptin may occur. Neutralizing antibodies could inhibit endogenous leptin action and/or result in loss of metreleptin efficacy.
4. Hypoglycemia: Metreleptin administration may increase the risk of hypoglycemia in patients treated with insulin or insulin secretagogues by improving insulin sensitivity. Patients will be cautioned about the possibility of hypoglycemia and all patients will receive education about signs and symptoms of hypoglycemia within the first week of the study

spent in the hospital. Diabetic patients will be measuring their glucose concentrations four times a day throughout the study and background therapy will be tailored to prevent hypoglycemia. Also we will explain this potential risk to the local physicians caring for the patients.

5. **T-cell lymphoma:** T-cell lymphoma has occurred in patients with acquired generalized lipodystrophy, both with and without metreleptin treatment. There is no data to support an increased risk of T-cell lymphoma (with or without metreleptin) in patients with mutations of the insulin receptor who may participate in this study.
6. **Autoimmunity:** Autoimmune disorder progression has been observed in patients with lipodystrophy treated with metreleptin, although a causal relationship with metreleptin has not been established. There is no data to support an increased risk of autoimmunity or autoimmune disease progression (with or without metreleptin) in patients with mutations of the insulin receptor who may participate in this study.
7. **Papillary thyroid carcinoma:** While on metreleptin therapy, three patients with severe insulin resistance due to either lipodystrophy or mutations of the insulin receptor developed papillary thyroid cancer. Another three patients with severe insulin resistance (again, lipodystrophy or insulin receptor mutations) developed papillary thyroid cancer but were never treated with metreleptin. Papillary thyroid cancer is a common cancer, and thus it is not yet clear if we are observing a true increased incidence, or if this represents population background risk, plus increased detection due to screening. There are epidemiologic data from patients with obesity or type 2 diabetes suggesting that insulin resistance may be a risk factor for papillary thyroid cancer. We do not know if metreleptin can promote growth of papillary thyroid cancer. Since patients with insulin resistance may be at higher risk for developing papillary thyroid cancer, we will screen subjects for this using ultrasound. They will have an ultrasound of their thyroid performed with their baseline visit, and at routine NIH follow-up visits if clinically indicated.
8. **Weight loss:** Metreleptin frequently leads to weight loss, particularly at the high doses used in this study. Body weight will be monitored per protocol, and doses of metreleptin adjusted to avoid severe weight loss.
9. **Hair loss:** 3 patients with lipodystrophy noted hair loss on metreleptin. The hair loss was a small amount, but the patients noticed it was a little more than what is typically lost in one day (around 100 hairs). One of the three patients noted the hair loss started before she started metreleptin. Two other patients on the study had significant hair loss, years before they started the study, to the extent that they need to wear wigs. It is not known if hair loss was related to metreleptin, part of the syndrome of lipodystrophy, or associated with insulin resistance and hormonal imbalances.
10. **Other:** Other frequently reported adverse events have been headache, fatigue, nausea and influenza-like symptoms. With the studies conducted so far, there have been no consistent patterns of changes noted in hematological parameters, ALT, AST, BUN, albumin and CPK values.

OTHER RISKS:

The total amount of blood drawn from the patients will be kept within the NIH Clinical Center restrictions. In adult patients, total amount of blood to be drawn with the outlined studies is estimated not to exceed 200 cc per 6-week period, which is well below the Clinical Center limit of 550 cc per 8-week period for research patients. Adjustments will be made in blood volumes for pediatric patients as necessary not to exceed the limit set by the following formula: (body weight (kg) x 9.5) cc blood per 8-week period.

Each blood draw is associated with pain and risks of infection though these risks are minimal. In routine care, the frequency of scheduled blood draws for any stable diabetic patient with current standards is at least 2-4 times a year. In this study, patients are asked to have a blood draw every 6-12 months.

The oral glucose tolerance test may cause nausea and requires placement of an IV catheter for blood draws. Ultrasound tests are not associated with any risk other than the discomfort of an ultrasound probe over a full bladder in female patients undergoing pelvic ultrasonography.

Some patients may find the time needed to complete the research studies an inconvenience in their routine lives. Each participant in the study will clearly understand that participation is totally voluntary.

Another source of inconvenience involved in this study is the necessity of 24-hour urine collections. However, this will facilitate assessment of long-term glucose control without the lag time that is usually observed with relying on HbA1c values.

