1.2 SCHEMA

1.3 SCHEDULE OF ACTIVITIES (SOA)

Baseline Visit (3-4 days): Patients will be admitted to the research center.

They will have their history and physical examination completed on the day of admission. Following a 12 hour fast, the OGTT will be performed. In addition, patients' capillary blood glucose will be measured before each meal and at bedtime. 24-hour glucosuria (and other 24 hour urine studies) will also be determined. After baseline testing has completed, patients will be trained in the proper storage, preparation, and administration of metreleptin injection, and will begin metreleptin injections subcutaneously during the hospitalization. Therapy will begin at determined efficacious dose for this group of patients of (0.2 mg/kg/day for male and female patients). For patients who reside outside the US, sufficient drug supply will be sent home with the patient to last until the next scheduled visit. For patients who reside within the US, a 3 month supply of drug will either be sent home with the patient or shipped to the patient's home.

Months 6 and 12 and every 6 months thereafter (3-4 days): At the end of 6 months, patients will return to the Clinical Center for collection of the same data obtained at baseline. For patients for whom it is challenging to travel to the Clinical Center every 6 months (i.e. ex-US patients), visits may be conducted every 12 months after the first year per investigator discretion. In the event that circumstances beyond our control preclude the travel of one or more of the study participants to the NIH Clinical Center for a visit, or otherwise would put their health at greater risk (i.e. epidemic or pandemic), we will endeavor to establish capabilities for remote visits. Specifically, the study team will request local laboratory studies to be done, to include, at a minimum, basic chemistry panel, CBC with diff, hemoglobin A1c, and pregnancy testing in female subjects with reproductive capacity, and conduct a telehealth/telephone visit with the patient. Telehealth/telephone visits will adhere to HHS guidance (<https://www.hhs.gov/hipaa/for-professionals/special-topics/emergency-preparedness/notification-enforcement-discretion-telehealth/index.html>) and can use all telehealth modalities under the good faith provision during a pandemic/epidemic as allowed by HHS for care of study participants.

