6.1.2.3 Dose Modifications

Patients will monitor body weight at home weekly for the first 3 months of treatment. In addition, weight is monitored at each follow up visit. Doses of metreleptin will be adjusted based on body weight to maintain a consistent dose of metreleptin within the range of 0.18-0.24 mg/kg/day. If body weight decreases by more than 15%, then a dose reduction (by 0.02 mg/kg/day) will be made. If a dose change is made, patients will monitor body weight at home monthly for the next 3 months and additional dose adjustments will be made as needed.

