8.4.4 Time Period and Frequency for Event Assessment and Follow-Up

The occurrence of an adverse event (AE) or serious adverse event (SAE) may come to the attention of study personnel during study visits and interviews of a study participant presenting for medical care, or upon review by a study monitor. At each study visit, the investigator will inquire about the occurrence of AE/SAEs since the last visit.

Study staff will record all reportable events with start dates occurring any time after informed consent is obtained until 7 (for non-serious AEs) or 30 days (for SAEs) after the last day of study participation. Any significant worsening noted during interim or final physical examinations, electrocardiogram, x-ray filming, any other potential safety assessment required or not required by protocol should also be recorded as a non-serious or serious AE, as appropriate, and reported accordingly.

Abbreviated Title: Effects of leptin in insulin resistance

Version Date: AM N ver. (approved 10/21/20); rev for AM O (5/5/21)

Laboratory Test Result Abnormalities

The following laboratory test result abnormalities will be captured as non-serious AE or SAE as appropriate:

1. Any laboratory test result that is clinically significant or meets the definition of an SAE
2. Any laboratory test result abnormality that required the subject to have study drug discontinued or interrupted
3. Any laboratory test result abnormality that required the subject to receive specific corrective therapy.

It is expected that wherever possible, the clinical rather than laboratory term would be used by the reporting investigator (e.g., anemia versus low hemoglobin value).

Any medical condition that is present at the time that the participant is screened will be considered as baseline and not reported as an AE. However, if the study participant's condition deteriorates at any time during the study, it will be recorded as an AE.

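### Adverse events are actively asked about only at study visits, the first after baseline at month 6, so mild early reactions may be under-ascertained and poorly dated

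*Combined protocol and SAP*

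**What the plan says.** - **The reaction (2.3.1).** Injection site reactions are the most frequent adverse events, at 40% on drug against 15% on placebo in previous studies. On severity and timing: "The majority were reported as mild in severity with average time of onset of 15 days". In some subjects investigators saw "gradual decreases in severity over time to complete disappearance of injection site reactions during continuous study-drug administration". No spread of onset times and no duration is given. Bruising at the site is listed separately: "Mild to moderate injection site ecchymosis was reported in 56% of all subjects", without an onset time.
- **The visits (1.3).** Injections begin during the baseline admission. That stay is given as 3-4 days in one place and as a week in another; the two should be reconciled, but both end before day 15. The next scheduled visit is month 6. The schedule table has no column in between and no adverse event row.
- **The inquiry (8.4.4).** "At each study visit, the investigator will inquire about the occurrence of AE/SAEs since the last visit". The other routes named are a participant presenting for care and review by a study monitor.
- **Contacts before month 6.** Section 6.1.2.3: "Patients will monitor body weight at home weekly for the first 3 months of treatment". Section 1.3 adds telephone or telehealth communication to adjust glucose-lowering therapy, unscheduled visits for safety or clinical care, and a 3-month drug supply for US patients. None of these is described as an occasion to ask about adverse events.
- **What is to be recorded (9.4.4).** All adverse events, with start date, stop date and severity, although documentation is left to the investigator's discretion.

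**The concern.** Section 2.1 sets out to test safety as well as efficacy, and section 9.3.1 makes every participant evaluable for toxicity from the first treatment. With a single arm (4.2), the safety description is simply the observed event rate and timing, and both depend on how and when patients are asked.

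By the protocol's own account, the commonest reaction usually starts after discharge, is mostly mild, and in some patients is gone later. Those features make an event easy to forget or not to mention. The first scheduled question comes at month 6. Recall may be weaker than usual here: section 5.3 expects most patients to be under 18 and notes that cognitive impairment appears more prevalent. A patient who stops early, misses month 6 and cannot be reached (7.3) might never be asked directly.

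At stake are the incidence, onset date, duration and severity of mild early reactions. The HbA1c result is not at stake.

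**Working it through.** The plan states no figure on this point, so there is none to reproduce. The check is a date calculation, followed by an illustration that rests on an assumption.

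**Step 1: is the patient at home at the mean onset?** The first dose is given in the baseline admission, which lasts 3-4 days or about 7 days depending on the sentence in 1.3. Mean onset is day 15 (2.3.1). Since 15 > 7, yes.

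**Step 2: time from mean onset to the first scheduled inquiry.** Month 6 = 365.25 / 2 = 182.6 days. Gap = 182.6 − 15 = 167.6 days, about 168. In months: 167.6 / (365.25 / 12) = 167.6 / 30.4 = 5.5.

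**Step 3: what incomplete recall would do (illustration only).** The documents give no recall figure. Let *s* be the assumed share of patients with a reaction who still report it at month 6.

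- Expected recorded cases = n × 0.40 × s
- Chance of recording at least one case = 1 − (1 − 0.40s)^n

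The accrual ceiling is 20, of whom 11 are enrolled (5.6), which leaves 20 − 11 = 9.

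| Assumed s | Recorded, n = 20 | Observed rate | Recorded, n = 11 | Recorded, n = 9 | Chance of at least one, n = 20 |
|---|---|---|---|---|---|
| 100% | 8.0 | 40% | 4.4 | 3.6 | >0.99 |
| 75% | 6.0 | 30% | 3.3 | 2.7 | >0.99 |
| 50% | 4.0 | 20% | 2.2 | 1.8 | 0.99 |
| 25% | 2.0 | 10% | 1.1 | 0.9 | 0.88 |

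The observed-rate column is just 40% × s, so it restates the assumption and is not evidence of its size. The last column is more useful: even at 25% recall the reaction would very probably be seen at least once. What is exposed is how often, when, for how long and how severely it occurs, rather than whether it is noticed.

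**Step 4: do the day-15 and 40% figures carry over?** They come from earlier studies. Section 2.3.1 also says that higher doses seemed to bring more reactions, and earlier ones, and describes the doses in this study as high. If that holds here, onset could be earlier and the recall interval slightly longer than 168 days.

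**The case against.** The strongest reply is that nothing in the documents shows a loss of events. The month-6 question looks back over the whole interval since the last visit. Events can also surface through presentation for care, monitor review and unscheduled visits, and 8.4.4 requires significant worsening on any safety assessment to be recorded. Section 5.4 counts telehealth and telephone visits as visits, so the existing inquiry arguably covers those already. Every scheduled visit includes an interim history and a physical examination with emphasis on the skin (8.2.1). A reaction still present at month 6 would therefore be found, and disappearance is reported only in some subjects.

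This reply stands against three stronger readings that a reader might infer:

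- *Early harm is under-counted.* Not shown. The documents support a risk of under-ascertainment, of unknown size.
- *Hypoglycemia goes unobserved before month 6.* Not supported. Section 2.3.1 has diabetic patients measuring glucose four times a day throughout. Section 1.3 asks insulin users for at least two checks a day and does not ask others for routine home checks. These passages differ and must be reconciled, but under either one insulin users check their glucose.
- *The gap grows to nearly a year when visits are 12 months apart.* The 15-day figure is an average onset for the drug reaction. It cannot be counted from a visit made after a year of treatment. The 12-month spacing is also limited to patients for whom travel is difficult, at the investigator's discretion.

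Three further points on the other side are fair. Safety is not a listed endpoint (section 3). The numbers are small: even 8 of 20 has an exact 95% interval of about 19% to 64%, which contains the 20% and 30% rates in the illustration. And 11 patients are already enrolled, so the early period can be improved for about 9.

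The reply does not remove the core of the point. The routes before month 6 are passive or conditional, and no diary, scheduled call or early safety contact is described. A look-back of up to six months is a weak basis for the start and stop dates that 9.4.4 asks for when the event was mild and has resolved.

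**Conclusion.** The point holds as a weakness of ascertainment. As written, active inquiry takes place only at study visits, and the first after the baseline admission comes about 168 days (5.5 months) after the mean onset of the commonest reaction. Incidence, onset date, duration and severity of mild, early, transient reactions therefore rest on long recall or spontaneous report and may be under-ascertained.

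The interval follows from the documents, on the assumption that the 15-day mean from earlier studies applies here. The number of events lost cannot be computed from them; the recall shares in the table are assumptions. Serious or medically attended events are less exposed, because other routes are likely to bring them to notice. The primary HbA1c comparison is unaffected. The change is worth making because it is cheap and the protocol states a safety aim, not because a loss has been demonstrated.

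**What to change.** 1. In 8.4.4, extend the inquiry from study visits alone to *each study visit and each telephone, telehealth or drug-resupply contact*. Use a short checklist: injection site reaction, hypoglycemia, rash or allergy, other, each with start and stop dates.
2. Collect the same items with the home weights of months 0 to 3 (6.1.2.3).
3. Add an adverse event row to the schedule of activities in 1.3.
4. In 9.4.4, report early-onset events by collection method. It would help to say there that checklist entries are always documented, since a checklist does not by itself remove the investigator's discretion over documentation.

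**Cost.** A protocol wording change, one form, and a small added log for patients and families. The log is a new task: 6.1.2.3 describes weighing at home but no record returned to staff. Drug may also be shipped, so a resupply is not always a conversation and someone would have to make the contact. No new clinic visit is needed. The benefit falls mainly on the roughly 9 patients still to be enrolled. The cohort will then contain two collection methods, which is why early events should be shown separately by method rather than pooled.

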At each follow up visit, for patients who reside outside the US, sufficient drug supply will be sent home with the patient to last until the next scheduled visit. For patients who reside within the US, a 3 month supply of drug will either be sent home with the patient or shipped to the patient's home (US patients only).

Unscheduled visits, due to safety or clinical care, may also be conducted remotely through telehealth/telephone and may include offsite laboratory and radiologic studies and/or in conjunction with a local physician with the supervision of the study PI. Laboratory and imaging results will be sent to the study team for safety monitoring and clinical care. During a pandemic affecting patient travel, serial missed research collections will not be considered major study deviations and will be reported to the IRB at the time of continuing review. Laboratory and imaging results obtained outside of the NIH may be incorporated into the study data set for both safety and efficacy.

During this time, patients remain on the full predicted dose. At each of these subsequent visits, the patients will have their blood drawn collecting the same labs that were obtained at baseline, and including serial metabolic testing such as the OGTT.

Abbreviated Title: Effects of leptin in insulin resistance

Version Date: AM N ver. (approved 10/21/20); rev for AM O (5/5/21)

If after 12 months of treatment it is determined by the principal investigator that the patient has shown improvement metabolically (improved HgbA1c, FBS, fasting insulin level), we will continue to follow the patient indefinitely on leptin therapy until such time that the leptin is approved through the FDA and/or the patient does not wish to continue on the study.

The study will involve an initial week hospitalization for each recruited patient. Thereafter, the patients will return to the Clinical Center as in-patients for assessment and data collection in accordance with the program every 6-12 months. Pre-existing glucose lowering therapies will be adjusted as needed to prevent hypoglycemia per standard clinical practice by communication between qualified study staff and the patient (telephone, telehealth, etc.). Patients taking insulin are asked to check their blood sugars at least 2 times a day (before breakfast and before another meal or at bedtime). Patients not taking insulin are not asked to routinely monitor their glucose levels while at home.

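### Two safety rules are inconsistent within the protocol: 5.2 omits the anaphylaxis restriction in 2.3.1, and 1.3 does not request the glucose checks promised in 2.3.1 from patients on insulin secretagogues

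*Combined protocol and SAP*

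**What the plan says.** **Anaphylaxis.** The hypersensitivity item in 2.3.1 names two groups who should not receive metreleptin: those with past anaphylaxis or an anaphylactic-type reaction, and those hypersensitive to proteins derived from E. coli. Section 5.2 lists eight exclusions. Item 8 is the E. coli restriction, and no item mentions anaphylaxis. Item 7 leaves it to the investigators to exclude for other conditions that would get in the way of finishing the study. Section 7.2 gives a life-threatening systemic allergic reaction to metreleptin as an example of a reason to withdraw a participant.

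**Glucose monitoring.** The hypoglycemia item in 2.3.1 says metreleptin "may increase the risk of hypoglycemia in patients treated with insulin or insulin secretagogues" and offers as one protection that "Diabetic patients will be measuring their glucose concentrations four times a day throughout the study". Section 1.3 sets a different schedule for home: "Patients taking insulin are asked to check their blood sugars at least 2 times a day", but "Patients not taking insulin are not asked to routinely monitor their glucose levels while at home". Section 6.5 adds metreleptin to whatever glucose-lowering therapy the patient already takes. It excludes no drug class and permits adjustment after the first year.

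**The concern.** A risk section describes protections, and the eligibility list and schedule are what staff work from. Where they differ, the protection may not reach the patient.

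For anaphylaxis, someone can pass every criterion in 5.2 and still belong to a group that 2.3.1 says should not be given the drug. Enrollment was still open in this version: 5.6 reports 11 enrolled of an anticipated 20, so 5.2 would govern up to 20 − 11 = 9 further entrants.

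For glucose, home checks are the only listed safeguard that produces routine readings between visits. Under 1.3 a secretagogue user would not be asked for them. Detecting lows from symptoms alone is a weak substitute in this population: 5.3 expects most participants to be minors and reports more frequent cognitive impairment, possibly linked to earlier hypoglycemia that went unnoticed. Section 7.2 also allows withdrawal for not complying with self-monitoring, and the two sections define that duty differently.

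**Working it through.** There is no plan figure to reproduce. The check is a comparison of sections, with one small calculation.

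**Step 1: anaphylaxis.** Restrictions on dosing in the hypersensitivity item of 2.3.1: 2. Carried into 5.2: 1 (E. coli). Exclusions in 5.2 that name anaphylaxis: 0 of 8. Two provisions might fill the gap, and neither fully does. Item 7 of 5.2 depends on investigator opinion and is framed around completing the study. The example in 7.2 operates only once a participant has been dosed and has reacted.

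**Step 2: glucose checks per day, by therapy.**

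| Diabetic patients | 2.3.1 | 1.3 (home) | Named at risk in 2.3.1? | Result |
|---|---|---|---|---|
| On insulin | 4 | at least 2 | yes | compatible, since 2 is a floor, but the minimum differs |
| On a secretagogue, no insulin | 4 | 0 routine | yes | conflict in a named risk group |
| On neither | 4 | 0 routine | no | mismatch of wording |

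**Step 3: could the four-a-day rule mean inpatient testing?** At the baseline admission "capillary blood glucose will be measured before each meal and at bedtime", which is 3 + 1 = 4 a day, and the follow-up visits collect the same data. Admissions last 3 to 4 days each under 1.3, although the same section also says "The study will involve an initial week hospitalization for each recruited patient".

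- Low count for year 1 (baseline, month 6, month 12): 3 + 3 + 3 = 9 days, and 9/365 = 2.5%.
- High count: 7 + 4 + 4 = 15 days, and 15/365 = 4.1%.

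Testing on 2.5% to 4.1% of the days cannot be what 2.3.1 describes, since its wording covers the whole study. After year 1 the gap between admissions can grow, because for patients who find travel hard "visits may be conducted every 12 months after the first year per investigator discretion".

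**Step 4: can the conflicting group exist?** Yes. Section 6.5 excludes no class of glucose-lowering drug. Whether anyone enrolled belongs to the group is not stated.

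**The case against.** The strongest reply is that little may turn on either gap.

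- **The affected group may be empty.** Sections 2.1 and 2.2 describe severe hyperinsulinemia and very large insulin doses, and no section reports a patient taking a secretagogue. This stands. A reader might infer that at-risk patients are going unmonitored; the documents show only that 1.3 would permit it.
- **Section 1.3 forbids nothing.** It has therapy adjusted to prevent hypoglycemia through contact with staff, which leaves room for individual monitoring. Section 2.3.1 adds education and informing local physicians, and 6.5 adds tapering and instruction. These are real safeguards, but none yields routine readings between visits.
- **Section 2.3.1 is itself protocol text.** An investigator who follows it would not dose a patient with past anaphylaxis, and such a patient arguably could not complete the study under item 7 of 5.2. First doses are also given in hospital. This partly stands, so one cannot infer that such a patient would in fact be treated. But it relies on staff looking beyond the eligibility list, when the companion restriction was thought worth listing there.
- **Scope.** Section 2.3.1 does not say what the anaphylaxis was to. That is a reason to define the criterion, not to leave it out.

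A reader might also infer that hypoglycemia risk rises after year 1, when the bar on increasing glucose-lowering doses ends. Section 6.5 links that bar to the period of primary outcome assessment. It protects the endpoint and is not offered as a hypoglycemia safeguard, so its ending supports no such argument.

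**Conclusion.** Both inconsistencies are present in the current text. One of the two dosing restrictions in the hypersensitivity item of 2.3.1 is absent from 5.2. For diabetic patients not on insulin, the two monitoring rules are four checks a day against no routine home checks. The monitoring conflict has a safety consequence only for secretagogue users, whose number is not given and could be 0. For insulin users the rules can be met together, and for diabetic patients on neither drug the difference is one of wording.

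The point rests on reading 5.2 as the operative eligibility list and 1.3 as the operative home schedule. It does not touch power, type I error or the HbA1c analysis. This is a minor safety-consistency correction, worth making because it is cheap and secures protections the protocol already states.

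**What to change.** 1. **Section 5.2.** Add the anaphylaxis restriction from 2.3.1 as an exclusion. The sponsor should define its scope, for example which causes of anaphylaxis count, and use the same words in both sections. The cost is that a rare patient may be turned away from a study capped at 20. A defined scope limits this to the cases intended, and 2.3.1 already says such a patient should not be dosed.

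2. **Sections 1.3 and 2.3.1.** Extend the home-monitoring request in 1.3 to patients on an insulin secretagogue. State one frequency in both sections for patients on insulin or a secretagogue. The sponsor should choose between four a day and at least two a day and give the reason. The documents offer no basis for preferring two, so the 2.3.1 figure should not be lowered by default. Also say in both places what is expected of diabetic patients on neither drug. The cost is testing supplies and daily burden for any patients affected, plus the burden on insulin users if four a day is chosen.

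Both changes are amendment wording and fit in one amendment.
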